2.6 Feasibility: Pilot Study

To ascertain current practices and support for this trial, we surveyed all members of both ANZCA and ANZICS Trials Groups (n=238) and found that >90% were comfortable with the proposed Group fluid regimens and were interested in participating in the trial (60).

We undertook a feasibility pilot study of the proposed trial at 3 centres. After ethics approval and patient consent, and surgeon, anaesthetist and intensivist support, we have demonstrated that we can successfully implement the fluid regimens both intraoperatively and postoperatively:

variable	Restrictive (n=41)	Liberal (n=41)	P value
Age, y	65 ± 12	67 ± 12	-
IV fluid (crystalloid + colloid)			
Intraoperative	1746 ± 748	2730 ± 1309	<0.0005
Total at 24 h postoperative	3167 ± 1625	5133 ± 2138	<0.0005
Postoperative			
Haemoglobin, g/L	110 ± 18	101 ± 17	0.014
Albumin, g/L	31 ± 6.7	27 ± 7.0	0.030
CRP, mg/L	108 ± 80	128 ± 75	0.33
Quality of recovery score	159 ± 20	154 ± 26	0.34
Median ICU stay, h	0 (0-15)	0 (0-19)	0.86
Median Hospital stay, days	8.1 (5.6-14)	8.4 (6.9-16)	0.30

To date there is no evidence of any adverse haemodynamic or renal effects with restrictive therapy (61).

In addition, we are currently undertaking a cohort study of 400 patients undergoing a range of elective surgeries to accurately measure and define rates of comorbidity, wellbeing and disability at 1, 3, 6, and 12 months after surgery. This will validate our follow-up and disability measurement techniques.

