- 12. **Any blood transfusion:** including red cell, fresh frozen plasma or platelet transfusion, from the commencement of surgery
- 13. Unplanned admission to ICU within 30 days of surgery
- 14. Total ICU stay: additive, including initial ICU admission and readmission times up to Day 30
- 15. **Hospital stay:** additive, from the start (date, time) of surgery until actual hospital discharge , plus readmission(s) up to Day 30
- 16. Quality of recovery: QoR-15 score(76) on days 1, 3, and 30.
- 17.

Excessive fluid resuscitation can cause haemodilution (64) and dilutional coagulopathy, and this may increase the need for red cell and other blood transfusion (32). Blood transfusion is, of itself, associated with increased rates of sepsis and other postoperative complications (3, 24). All patients will have the same red cell transfusion trigger of 70 g/L, but this can be modified after assessment of cardiovascular risk (77, 78) or concern for active bleeding. Normal Saline, containing 154 mmol of sodium and 154 mmol of chloride per litre, is non-physiological and can lead to hyperchloraemic acidosis (33) and perhaps poorer outcome (79, 80). We will use a balanced salt solution as the routine fluid therapy in this study. The questionable value of urine output as a measure of kidney or other tissue perfusion will be emphasized (81).

Our study Group fluid regimens are aimed at distinct volume differences and according to recent recommendations (4, 72). The group-assigned fluid regimens will continue for at least 24 hours after surgery, or until cessation of IV fluid therapy (whichever occurs first). If the patient's clinical condition warrants modification to the type or rate of fluid administration, then such modifications can be made immediately. This does NOT imply that the patient is removed from the trial because we will analyze according to the intention-to-treat principle, but we will collect such data for secondary per-protocol and sensitivity analyses.

Management of Oliguria

It is a normal response of the body to attempt to conserve fluid in times of physiological stress. Oliguria (low urine output) is part of this homeostatic mechanism; there is no evidence it is harmful in the short term (first 24-48 h after surgery is common and not abnormal) (81). Nor is there any evidence that diuretics protect against AKI (82). We will however provide guidance to ward medical and nursing staff (see Procedures Manual).

4. Experimental control

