adjusted creatinine = serum creatinine × (1 + cumulative fluid balance/total body water), and assuming that total body water is 60% of body weight, expressed in mL. Serum creatinine is measured on days 1 and 3 and the maximum value in the patient's hospital stay. We will apply adjustments to creatinine levels at days 1 and 3 only. Fluid intake will be accumulated using IV fluids administered intraoperatively, in recovery, and on days 1 to 3 postoperatively, plus the volume of any blood transfusions administered. Fluid outputs from the time of surgery to Day 1 post-surgery will be accumulated using the recorded urine outputs, blood losses and volumes in surgical drains. Missing fluid output components will be imputed to prevent adjustment factors being missing when creatinine levels are present. Fluid outputs on days 2 and 3 are not recorded, so these will be estimated under the assumption of a net fluid balance of zero on each of days 2 and 3; this will form the principal analysis. Sensitivity to this assumption will be assessed using two alternatives: (a) assuming a zero cumulative fluid balance at day 3, and (b) assuming the ratio of intake to outputs up to day 1 persists on days 2 and 3. These two assumptions enclose that of the principal analysis.

We will also report the use of renal replacement therapy up to 90 days after surgery; and delta-creatinine, defined as the difference between the maximum (fluid-adjusted) postoperative serum creatinine level and the preoperative serum creatinine level.

- 4. Pulmonary oedema: documented evidence of respiratory distress or impaired oxygenation and radiological evidence of pulmonary oedema.
- 5. Duration of mechanical ventilation: Defined as additive over all episodes up to 90 days after surgery. This will be reported as (a) the proportion of patients requiring ventilation; and (b) the duration of ventilation in patients receiving ventilation.
- 6. Inflammation: plasma C reactive protein concentration on day 3 after surgery.
- 7. Tissue perfusion marker: peak serum lactate concentration within 24 hours of surgery.
- 8. Any blood transfusion: including red cell, fresh frozen plasma or platelet transfusion, from the initiation of surgery; and quantity of transfusion in patients receiving each product.
- 9. Unplanned admission to HDU/ICU within 30 days of surgery.
- 10. Total HDU/ICU stay in patients admitted to HDU/ICU, including initial admission and readmission duration up to day 30

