Duration and length of stay outcomes (5, 10, 11) will be summarised using medians and interquartile ranges, and compared across treatment arms using the Wilcoxon– Breslow– Gehan test, with length of stay in hospital and in intensive care censored at 30 days, and with in-hospital deaths assigned the highest length of stay.

Outcomes measured on a continuous or semi-continuous scale (6, 7, 8, 12) will be summarised by means and standard deviations if reasonably symmetrically distributed and compared between treatment arms using linear regression with robust standard errors. Skewed outcomes will be summarised by medians and interquartile ranges; right skewed outcomes will be log-transformed prior to analysis using linear regression, and left skewed outcomes will be analysed using median regression with robust standard errors.

Additional sensitivity analyses

Sensitivity analyses for all outcomes will use regression models with additional adjustment for the stratification variables of site and planned HDU/ICU destination status, plus any variables exhibiting substantial imbalance across treatment arms at baseline. Sensitivity to missing outcome data will be performed using multiple imputation if the proportion of missing data for the particular outcome is >5%. These analyses will use multiple imputation, employing imputation models with baseline and auxiliary post-baseline variables, and results combined across imputations using Rubin's rule.

Subgroup analyses

Planned subgroup analyses will assess heterogeneity of treatment effects of the primary endpoint across patient sex, age groups (approximate quartiles), country, bowel surgery (yes/no) and intraoperative use of any goal-directed techniques (yes/no). The latter include invasive or non-invasive cardiac output, stroke volume or pulse pressure variation and oesophageal Doppler, but exclude central venous pressure monitoring.

Additional prespecified subgroups will be tested for heterogeneity of effect, and their results considered exploratory: BMI categories (defined as underweight <18.5, normal 18.5-25, overweight 25-30, obese 30-35, super obese >35), ASA physical status (1/2, 3, 4), preoperative planned HDU/ICU destination status, duration of surgery (approximate quartiles), and pre-operative planned use of a goal directed device (excluding CVP monitoring).

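### HDU/ICU stay, ventilation duration and transfusion quantity are tested only among patients who used each resource, so these three tests are not randomised comparisons and could mislead if allocation changes who uses it

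*SAP*

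**What the plan says.** Three items in the SAP list of secondary endpoints are defined on users only:

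- Item 5(b): "the duration of ventilation in patients receiving ventilation". Part (a) of the same item reports the proportion ventilated.
- Item 8, second part: "quantity of transfusion in patients receiving each product". The first part is any transfusion.
- Item 10: "Total HDU/ICU stay in patients admitted to HDU/ICU, including initial admission and readmission duration up to day 30".

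Under Other outcomes the SAP makes these formal comparisons: "Duration and length of stay outcomes (5, 10, 11) will be summarised using medians and interquartile ranges, and compared across treatment arms", by the Wilcoxon–Breslow–Gehan test. Stays are censored at 30 days and in-hospital deaths are given the longest stay. Item 8 falls under "Outcomes measured on a continuous or semi-continuous scale (6, 7, 8, 12"), which means linear regression, on the log scale if right skewed, or median regression if left skewed.

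Protocol 3.3.3.2 describes total ICU stay as "additive, including initial ICU admission and readmission times up to Day 30" and does not mention a restriction to admitted patients. The SAP's opening paragraph applies intention to treat to everyone randomised who has induction of anaesthesia for eligible surgery.

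**The concern.** Randomisation makes the arms alike at the start of surgery. It does not make alike the patients in each arm who later reach HDU/ICU, need a ventilator or receive blood. A regimen that keeps milder patients out of HDU/ICU leaves a sicker admitted group and can appear to lengthen stay. A regimen that brings in extra mild patients can appear to shorten it. In both cases the P value answers a different question from the one a reader will assume.

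The documents themselves give reasons why allocation might change membership of these subsets:

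- **Transfusion.** Protocol 3.3.3.2 says that generous fluid may raise the need for blood through haemodilution.
- **HDU/ICU.** Protocol 4.1 ties postoperative noradrenaline in the restrictive arm to an HDU/ICU setting, and unplanned admission is itself SAP item 9.
- **Ventilation.** The pooled results in Protocol 2.1 suggest fewer pneumonias (RR 0.43) and less pulmonary oedema (RR 0.22) with restriction.

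At stake are three secondary resource-use results, not the primary endpoint.

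**Working it through.** **1. Is there an all-patients version?** The documents give no planned figure for these three items, so there is none to reproduce. The SAP's coverage is as follows.

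| Item | Quantity tested in | Use of the resource tested in all patients? |
|---|---|---|
| 5 Ventilation | ventilated only | Proportion reported; item 5 is not in the list of binary outcomes (1, 2, 3, 4, 8, 9), so no test is assigned |
| 8 Transfusion | recipients only | Yes, risk ratio for any transfusion |
| 10 HDU/ICU stay | admitted only | Unplanned admission only (item 9); any admission is not an endpoint |

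No all-patients version of the three quantities is planned. The adjusted analyses and multiple imputation under Additional sensitivity analyses do not supply one, because non-users are excluded by definition and are not missing data.

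**2. Deaths.** The highest-stay rule for item 10 can act only on patients in the admitted set. A patient who dies without reaching HDU/ICU is left out. The rule is worded for length of stay, so it says nothing about ventilation or transfusion.

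**3. How large could the effect be?** Every rate and duration here is an assumption. Take 1500 patients per arm and a share p of users in the liberal arm. Stay is lognormal with median 24 h and log-SD 1. The restrictive regimen spares the fraction f of users with the shortest stays and lengthens nobody's stay. The labels could be swapped.

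The median among remaining users is the f + 0.5(1 − f) quantile of the original distribution:

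- f = 0.1: 0.55 quantile, 24 × exp(0.1257) = 27.2 h
- f = 0.2: 0.60 quantile, 24 × exp(0.2533) = 30.9 h

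So the users-only median rises from 24 h to about 31 h at f = 0.2. At p = 25%, mean hours per patient over the whole arm fall from 9.91 to 9.55 (simulated).

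Results from 1000 simulated trials per row (two-sided 0.05; with no censoring simulated, the Wilcoxon test stands in for the planned one):

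| p | f | Users-only test significant against the better arm | All-patients test (non-users 0) significant the right way |
|---|---|---|---|
| 10% | 0.1 | 30% | 14% |
| 25% | 0.1 | 63% | 21% |
| 40% | 0.1 | 85% | 28% |
| 10% | 0.2 | 81% | 43% |
| 25% | 0.2 | 99% | 74% |
| 40% | 0.2 | 100% | 84% |

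In these rows the all-patients test was significant the wrong way in at most 0.2% of trials. If remaining stays are also cut by 10% at f = 0.2, the users-only test still points the wrong way in 47%, 86% and 96% of trials (p = 10%, 25%, 40%). With f = 0 both tests hold about 5% two-sided error.

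**4. A gentler model.** Let a severity threshold decide admission, with stay rising with severity and treatment leaving any given patient's stay unchanged. The users-only test is then significant the wrong way in about 57% of trials at 30% v 20% admission, 17% at 30% v 25%, and 7% at 30% v 28% (2.5% expected by chance). A noisier admission rule lowers the first figure to about 27%. As a check, 24 h × exp(0.5 × severity + 0.7 × independent error), with admission noise equal in SD to severity for the last case, gives 58%, 17%, 5% and 28%.

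**5. Could recipient sets differ?** Pilot haemoglobin (Protocol 2.6) was 110 (SD 18) restrictive and 101 (SD 17) g/L liberal. The common trigger is 70 g/L and can be modified. If values were normal, the share below 70 would be Φ(−40/18) = 1.3% and Φ(−31/17) = 3.4%. This is only an indication that they could differ.

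**The case against.** Much of the plan limits the harm. Planned HDU/ICU admission is fixed before randomisation and is a stratification factor (Protocol 3.1 and 4.1), so most of the admitted set in item 10 may be the same whichever arm a patient joins. Any transfusion and unplanned admission are tested in all patients, the proportion ventilated is reported, and hospital stay (item 11) is tested without restriction with deaths ranked highest. A reader will therefore see incidence beside conditional duration. With many zeros, an all-patients rank test will also partly repeat the incidence comparison. All of this stands, and it limits the importance of the point. It does not turn the users-only P values into randomised comparisons.

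Three stronger readings are tempting, and the documents do not support them:

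- **That the subsets will differ in severity between arms.** This needs allocation to change who enters, which the documents suggest may happen but do not show. The pilot row "Median ICU stay, h" gives 0 (0–15) v 0 (0–19), P = 0.86. That is no sign of a large gap, though there were only 41 patients per arm.
- **That the size is known.** The high percentages in the table rest on sparing exactly the shortest stays. If users were spared at random with respect to stay, the users-only distribution would not shift. Nothing specific was modelled for ventilation or for transfusion quantity.
- **That the SAP contradicts the protocol.** Protocol 3.3.3.2 says how episodes are added up and is silent on the analysis set. A pilot table that includes zeros is not an analysis plan.

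**Conclusion.** The point holds in a limited form. Items 5(b), 8 (quantity) and 10 are formally compared in subsets defined after randomisation, with no all-patients counterpart, in a plan that otherwise follows intention to treat. Bias, including a result in favour of the wrong arm, is possible if allocation changes who is ventilated, transfused or admitted, and absent if it does not. For item 10 the exposure is mainly through unplanned admissions and planned admissions not taken up. The death rule for that item also misses patients who die outside HDU/ICU.

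The size cannot be read from the documents. Under the assumed models it runs from close to chance, when admission differs by 2 percentage points, to almost certain wrong-way significance under strong selection of short stays. The primary endpoint, mortality, the septic composite and acute kidney injury are untouched. The change is worth making because it is cheap and removes the selection.

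**What to change.** - **Items 5 and 10:** apply the planned Wilcoxon–Breslow–Gehan test to all analysed patients, with 0 hours for those not ventilated or not admitted. Check that the software keeps records with a time of 0. Keep the highest-rank rule for in-hospital deaths for HDU/ICU stay, where it will now reach every such death. State separately how deaths are handled for ventilation duration.
- **Item 8:** compare units of each product in all analysed patients, with 0 for non-recipients. Use a method that accepts zeros, such as a rank test or an untransformed mean difference with robust standard errors, because log-transformed regression cannot take them. Do not carry over the length-of-stay rule for deaths.
- **Users-only medians:** keep them as description, without P values, beside the proportion using each resource.

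The cost is revised SAP text, a new method for item 8, a death rule for ventilation, and the matching code. No new data are needed. The downside is that medians will often be 0, so means or rank statistics must be shown, and the all-patients tests will partly reflect incidence.

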3.2.2 Source and Number

We will use similar procedures to those used by us successfully in previous multicentre studies. Simple eligibility criteria, and research nurse-screening and enrolment, ensure that recruitment is maximized.

3000 patients in total will be required for this study (1500 in each group).

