4.1 Group assignment

This will be a large, randomized, parallel-group, controlled trial. After stratification by centre and planned ICU/HDU admission (or not), patients will be randomly assigned from a computer-generated list (1:1) to either a Restrictive or Liberal fluid Group.

A 24-hr interactive voice recognition system (IVRS) will be available. An alternative web-based randomisation service will also be available during the conduct of the trial.

This is an intention to treat trial. Any participant who is randomised will be followed for the duration of the trial (unless they withdraw consent) even if they are withdrawn from the active phase of the trial. Patients who do not complete the active phase of the study will not be replaced.

[figure not shown]
Liberal Protocol

The Liberal protocol group reflects common contemporary practices in Australia(29, 82), and is consistent with previous international trials (20, 24, 83) – see Appendix. At the commencement of surgery a bolus of Hartmann's balanced salt crystalloid 10 ml/kg followed by 8 ml/kg/h will be administered until the end of surgery – the latter can be further down-titrated after 4 hours if clinically indicated. Important: for the purposes of calculations of bolus and maintenance fluids in patients exceeding 100 kg, the maximal body weight will be set at 100 kg. A maintenance infusion will then continue at 1.5 ml/kg/h, for at least 24 hours, but this can be reduced postoperatively if there is evidence of fluid overload and no hypotension, and increased if there is evidence of hypovolaemia or hypotension. Alternative fluid types (crystalloid, dextrose, colloid) and electrolyte supplements will be allowed postoperatively in order to account for local preferences and patient biochemistry, for which we will collect data. For a 75-kg adult, the intraoperative volume (for a 4 h operation) will be 3150 ml (+colloid/blood replacement for blood loss), and then around 2700 ml per day. That is, the first (intraoperative + postoperative) 24-h fluid administration will be about 5400 ml (P.T.O).

Restrictive Protocol

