6. SAMPLE SIZE AND STATISTICAL ANALYSIS

All statistical analysis will be overseen by [name], Monash University Department of Epidemiology and Preventive Medicine. The intention-to-treat population will include all patients randomly assigned to groups AND undergoing induction of anaesthesia.

Our initial sample size calculation was based primarily on our own data and other published studies. Our ENIGMA-II trial (n>5000 enrolled to date), with a lower risk study population, has a disability-free survival rate of 70% (15% mortality, 15% new disability) at 1 year after surgery). The most recent large data comes from the UK, where the 1-year mortality for open colorectal surgery was 17% in the 31,847 patients with pre-existing comorbidity (84). Reductions in serious complication rates have exceeded 25% in pooled analyses of similar studies(3, 82), and pre-existing major comorbidity increases mortality risk up to 16-fold (83). Using a type I error of 0.05 and survival analysis, with an expected one year disability-free survival probability of 65% (65) and a hazard ratio of ≥1.25, 1300 patients in each group will provide 90% power. Target recruitment was set at 2800 patients to account for losses due to follow-up. The Trial Steering Committee met on the 30th June, 2016, to discuss the results of a data quality committee review and statistician's report of the accruing incidence of disability. With near-complete information on 2,578 enrolled patients there were 300 events (disability or death); that is, a 12-month event rate of 14.6% - this is lower than expected. An increase in the trial sample size to 3,000 (≈380 events), which provides 80% power to detect HR≤0.75. This protocol amendment was accepted by the Steering Committee.

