Additional analyses of the above subgroups will be performed for the endpoints of newonset disability, composite of 30 day mortality and septic complications, and acute kidney injury.

For these analyses, we will undertake tests for interaction by adding treatment-by-covariate terms to the regression models specified for the main analyses of each outcome.

SAMPLE SIZE RE-ESTIMATION

The original sample size calculation was as follows: Assuming a 12 month disability-free survival probability of 65%, 2650 patients were required to detect a hazard ratio of 0.80 with 90% power using the Freedman method for the sample size for a log rank test. Correspondingly, 850 events were expected to be observed. The sample size was inflated to a total of 2800 patients to account for withdrawals and loss to follow-up.

A sample size reassessment of the assumed primary endpoint event rate was performed after 2578 patients had been randomised. At that time there were 300 primary endpoint events with a 12 month event rate of approximately 15%. Increasing the target sample size to 3000 patients under this same event rate was expected to yield approximately 380 events and afford 80% power to detect a hazard ratio of 0.75.

REFERENCES

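### Beyond site and planned HDU/ICU admission, the adjusted sensitivity model selects covariates by observed baseline imbalance, not prognosis, and sets no metric, cut-off or candidate list

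*SAP*

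**What the plan says.** The primary comparison is an unadjusted Cox model containing treatment alone (Protocol section 6). A covariate-adjusted model then appears as a sensitivity analysis for all outcomes, in the same words in both documents (SAP, Additional sensitivity analyses; Protocol section 6, Sensitivity Analysis). It has two parts:

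- Site and planned HDU/ICU admission, the stratification variables. These are prespecified and always included.
- A data-driven addition: "plus any variables exhibiting substantial imbalance across treatment arms at baseline".

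Neither document says how large an imbalance must be to count as substantial, how it is to be measured, or which variables are candidates. No other prognostic covariate is prespecified for this model.

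On size and allocation, the protocol states "3000 patients in total will be required for this study (1500 in each group" (section 3.2.2) and "patients will be randomly assigned from a computer-generated list (1:1) to either a Restrictive or Liberal fluid Group" (section 4.1).

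**The concern.** This is a stated selection rule, not merely a list left unnamed. When allocation is random, a difference between arms at baseline arises by chance and says nothing about whether the variable predicts outcome. The rule therefore acts on the wrong property: a strong predictor that happens to balance stays out, and an irrelevant variable that happens to differ goes in. Supplying a threshold would make the rule reproducible but would not cure that.

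Two things are at stake. First, this is the only covariate-adjusted treatment comparison planned across all outcomes, so readers will use it as the robustness check on the unadjusted results. If its content depends on a cut-off that can be settled after arm-level data are seen, the check loses credibility. Second, the model forgoes whatever efficiency adjustment for known predictors would bring.

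**Working it through.** **Inputs.** From the documents: 1500 per arm, 1:1 allocation, "Using a type I error of 0.05 and survival analysis" (Protocol section 6; sidedness not stated, taken as two-sided), and "approximately 380 events and afford 80% power to detect a hazard ratio of 0.75" (SAP, Sample size re-estimation). Assumed, because the documents do not give them: the number of candidate variables (10 to 30), their independence, and all prognostic strengths.

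**1. The plan's own figures.** The documents give no figure for the imbalance rule, so the check starts from the stated power.
- Schoenfeld, 380 events, HR 0.75: z = √380/2 × 0.2877 − 1.96 = 0.844, power 80.1%. Freedman gives 79.5%. The stated 80% is reproduced.
- Original design, where the SAP says "2650 patients were required to detect a hazard ratio of 0.80 with 90% power using the Freedman method": events = (1.960 + 1.282)² × (1.80/0.20)² ≈ 852, and N = 2 × 852/(2 − 0.65 − 0.65^0.8) = 2656. The stated 850 events and 2650 patients are reproduced.

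The covariate rule enters none of these calculations.

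**2. Chance imbalance at this sample size.** The standard error of a standardised mean difference (SMD) is √(2/1500) = 0.0365. For cut-off t, the chance that one variable is flagged is p = 2 × [1 − Φ(t/0.0365)]. At t = 0.1 this is 2 × [1 − Φ(2.74)] = 0.0062. The chance that at least one of k independent variables is flagged is 1 − (1 − p)^k.

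| Cut-off | One variable | At least 1 of 10 | of 20 | of 30 |
|---|---|---|---|---|
| SMD > 0.05 | 17.1% | 85% | 98% | 99.6% |
| P < 0.10 (SMD > 0.060) | 10% | 65% | 88% | 96% |
| P < 0.05 (SMD > 0.072) | 5% | 40% | 64% | 79% |
| SMD > 0.1 | 0.62% | 6.0% | 11.6% | 16.9% |
| SMD > 0.2 | 0.000004% | about 0 | about 0 | about 0 |

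With 20 candidates, SMD > 0.1 adds nothing in 100 − 11.6 = 88.4% of trials. P < 0.05 adds 20 × 0.05 = 1 variable on average, whatever its prognostic value.

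**3. How often a real predictor gets in.** If five of the candidates are prognostic, at least one of them is flagged with probability 1 − (1 − 0.0062)^5 = 3% under SMD > 0.1 and 1 − 0.95^5 = 23% under P < 0.05. A simulation of 300 trials gave 4% and 22%.

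**4. What a fixed list could gain in the Cox model.** Two illustrations at HR 0.75 and about 380 events, both without site or HDU/ICU terms:
- 20 covariates, five of them prognostic at HR 1.4 per SD, 300 replicates. Power was 75.0% unadjusted, 75.7% with the SMD > 0.1 rule, 74.0% with the P < 0.05 rule and 78.0% with the five predictors fixed. Monte Carlo error is about 2.5 points per rate. Mean log HR was −0.277 unadjusted and −0.287 with the fixed list (true value −0.288). The mean SE was 0.1041 and 0.1043.
- One normal prognostic score, 1500 replicates. Unadjusted v adjusted power was 80.8% v 81.9% at SD 0.6 on the log-hazard scale, and 74.0% v 80.1% at SD 1.0. The SE of the log HR did not change.

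**5. Bias from leaving an imbalance alone.** An SMD of 0.1 in a covariate with HR 1.5 per SD multiplies the treatment HR by 1.5^0.1 = 1.041. On the log scale that is 0.04, against an SE of 2/√380 = 0.103.

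**The case against.** The strongest defence is that the adjusted model is a sensitivity analysis, not the powered test. Its purpose is to ask whether the unadjusted result survives adjustment for the strata and any visible chance imbalance. On that view, adding nothing in 88% of trials is benign, because there was nothing large enough to probe. This stands in part. But an imbalance can distort the result only through a variable that predicts outcome, so even for that purpose prognosis should decide which variables enter. A fixed prognostic list corrects for chance imbalance in the listed variables in any case.

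Several further points stand:

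- Adjustment did not shrink the Cox standard error in any of the simulations. The power gain comes from a coefficient less attenuated towards zero, that is, from moving to a conditional hazard ratio. Real precision gains are possible for outcomes analysed by linear regression (CRP, QoR-15) but have not been quantified.
- The scope for steering is small for any one variable: about 4% on the HR in step 5.
- The wording reads more naturally as a size of difference than as a P value, and 20 independent candidates is an assumption. Hence the ranges.
- An SD of 1.0 is a strong prognostic score, and nothing in the documents shows that the collected variables reach it.
- Some baseline information is already used through outcome definitions: AKI is a relative rise in creatinine, delta-creatinine subtracts the preoperative value, and the new-onset disability analysis uses change in WHODAS. The primary definition of disability, however, is an absolute WHODAS threshold, so baseline WHODAS is not accounted for there.

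**Conclusion.** The concern holds for the data-driven part of the model. Beyond the two stratification variables, covariates are chosen by chance imbalance under an unstated cut-off. Depending on that cut-off, the chance of adding at least one of 20 assumed independent candidates runs from about zero (SMD > 0.2) through 11.6% (SMD > 0.1) and 64% (P < 0.05) to 98% (SMD > 0.05). This is a low-severity improvement to the credibility and efficiency of the sensitivity analyses.

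Stronger readings that a reader might infer are not supported:

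- That the adjusted model picks all its covariates by imbalance, or adjusts for nothing useful. Site and planned HDU/ICU admission are always included, and the latter plausibly carries prognostic information, although the documents do not quantify it.
- That the primary result, its type I error or the stated 80% power is compromised. The primary model is unadjusted and the rule does not touch it.
- That the trial gives up a large and certain power gain. The figure is about 1 to 6 points for an assumed prognostic score SD of 0.6 to 1.0 at about 380 events. It is illustrative, applies only to the adjusted Cox model, and does not come from a smaller standard error.
- That the cut-off would in fact be chosen to suit the result. The documents leave this open and show nothing of the kind.

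**What to change.** Replace the imbalance clause in the SAP, and its twin in Protocol section 6, with a fixed list set before unblinding and used whatever the observed balance. Keep site and planned HDU/ICU admission, and add baseline predictors already collected: for example age (continuous), sex, ASA status and bowel surgery (yes/no), plus the outcome's own baseline value where one exists, such as baseline WHODAS for disability-free survival or preoperative creatinine for AKI. Present baseline imbalance descriptively only.

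The cost is one sentence. It needs no new data and no change to sample size or to the primary analysis. The one consequence for reporting is that the adjusted hazard ratio must be described as conditional on the listed covariates, because it estimates a somewhat different quantity from the unadjusted one and the two need not coincide even without imbalance.

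If the clause is kept, the minimum is to state the metric, the cut-off and the candidate variables before unblinding. That would remove the freedom to choose but would still select on chance.
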